### 2.2.3 Secondary Mechanistic Objectives

• To identify baseline autoantibody, cytokine/chemokine, and gene expression characteristics that are associated with an increased risk of SLE flare.

- To identify autoantibody, cytokine/chemokine, and gene expression characteristics present at Week 20 or changes in those characteristics from baseline to Week 20 that are associated with an increased risk of flare.
- To identify autoantibody, cytokine/chemokine and gene expression changes associated with withdrawal of MMF apart from flare.

Markers of particular interest include:

- Serologic markers: dsDNA antibodies, C3 levels, C4 levels, and antibodies toward Sm, ribonucleoprotein (RNP), SSA/Ro, & SSB/La;
- Presence/absence of a "B cell fingerprint" assessed by gene expression profiling;
- $\circ$  Presence/absence of an "Interferon- $\alpha$  biosignature" assessed by gene expression profiling;
- Levels of cytokines or chemokines associated with the interferon- $\alpha$  and  $\gamma$  pathway (measured by bead based assays or ELISA).

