### 3.1.1 Stratification, Randomization, and Blinding

Subjects will be randomized in a 1:1 ratio to either continue or withdraw from MMF. Given the relatively small number of subjects expected per site and the importance of ensuring balance on key disease-defining characteristics an adaptive procedure based on Frane [31] minimization concepts will be used to increase the likelihood of balance in treatment arms. The baseline characteristics that will be considered are study site, disease manifestation (renal disease, which will include subjects who presently have renal disease as well as those who have had renal manifestations in the past, versus non-renal disease, which will include subjects who have never had renal disease), and baseline MMF dose (< 2000 mg per day versus  $\geq 2000$  mg per day).

Subjects and investigational staff responsible for clinical care will not be blinded to the randomized treatment assignment. The cumbersome scheme that would have been needed to maintain the blind required that subjects take different numbers of pills from multiple bottles. Implementation of the scheme would have placed undue burden on the subjects and had a high potential for dosing errors. Knowledge of the assigned treatment also has the advantage of facilitating rapid response in the event of a serious flare.

Unblinding the trial has the potential to impact the estimated rates of disease reactivation, because the definition of this endpoint includes subjective elements. In order to assess the magnitude and direction of the impact on these estimates, a second blinded clinician will also conduct the physical exams scheduled for Weeks 8, 12, 16, and 20. If at Week 20, the subject has a mild/moderate or severe SELENA-SLEDAI flare, the blinded physician should also participate in the Week 24 visit. These time points were selected, because we anticipate that most flares will occur early in the study. The blinded physician will also receive any additional blinded subject records needed to complete the SELENA-SLEDAI and a questionnaire about the need to change medications. This information will be used to compare the rate of disease reactivation among blinded and unblinded assessors.

Statistical and project staff at the SACCC and the DAIT Medical Monitor and Project Manager will be unblinded to individual treatment assignments as well.

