#### 6.3.1 Serologic Markers

Serum for serologic markers including C3, C4, and antibodies to dsDNA, Sm, RNP, SSA/Ro and SSB/La will be collected at every scheduled visit and every Flare Visit.

C3, C4, and dsDNA antibodies (anti-dsDNA) are needed at each visit as part of the SELENA-SLEDAI\* scoring system, but will also be analyzed as independent markers to define the utility of the markers in predicting which subjects will meet the primary endpoint of clinical disease activation.

Antibodies to Sm, RNP, SSA/Ro, and SSB/La will be measured from a serum specimen at Baseline and Week 60 for all subjects. To evaluate these markers as predictors of flare, samples collected at pre-flare, flare, and post-flare time points may be analyzed for those subjects who flare. For subjects who do not flare, samples may be analyzed at three additional time points for comparison to the results for flaring subjects.

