# **Endpoint:**

For each subject, a yes/no variable will be assigned to indicate whether a subject has met the primary endpoint of clinically significant disease reactivation between Day 0 and Week 60, as defined above.

Subjects who terminate early from the study, and who had not previously met primary endpoint, will be handled as follows:

- 1. Subjects who do not have a mild/moderate or severe SELENA-SLEDAI flare at their last study visit will be categorized as not experiencing clinically significant disease reactivation.
- 2. Subjects who have a mild/moderate or severe SELENA-SLEDAI flare at their last study visit:
  - a. Subjects will be categorized as experiencing clinically significant disease reactivation for the following three scenarios:
    - i. Subject has a SELENA-SLEDAI mild/moderate or severe flare at the time of early termination, and a steroid increase/burst to ≥ 15 mg/day prednisone that is sustained through end of study.
    - Subject previously experienced a flare requiring either intraarticular, intra-muscular or IV steroids, or an increase/burst of steroids that was successfully tapered to < 15 mg/day within four

Version: 1.0 Page 18 of 48

<sup>1 For ALE06, prednisone > 0.5 mg/kg/day is categorized as a severe SELENA-SLEDAI flare if the duration is >2 weeks. Increases in prednisone >0.5 mg/kg/day but for ≤2 weeks will be categorized as mild/moderate SELENA-SLEDAI flares.

weeks, and is experiencing a severe flare at the time of early termination.

- iii. Subject has a SELENA-SLEDAI severe flare based on the following clinical components: SLEDAI score; New/Worse disease, and Increase in PhGA without considering prednisone or other treatments
- b. Subjects experiencing flare at the time of early termination, but who do not met the criteria in 2.a. above, will be classified as not experiencing clinically significant disease reactivation.

These cases will be re-categorized under sensitivity analyses for the primary endpoint (see 7.2.3).

The time of clinically significant disease reactivation is defined as the date of the first SELENA-SLEDAI assessment that meets (or goes on to meet) the criteria for clinically significant SLE reactivation. The time-to-event will be defined as the interval: date of disease reactivation – date of Day 0 visit. Subjects who do not experience clinically significant disease will be censored at the last visit date on study.

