# 7.4. Secondary Mechanistic Endpoints

#### 7.4.1. C3, C4, and anti-dsDNA Levels

**Endpoint**: C3, C4, and anti-dsDNA are run at baseline and every follow-up visit, including any Flare or Endpoint visits, during the course of the 60 week study period and run by a central laboratory.

Specifically, levels of C3, C4, and anti-dsDNA at Baseline, Week 20, at the time of first flare, and immediately prior to first flare will be analyzed.

**Analysis**: Descriptive statistics (mean, standard deviation, median, minimum, maximum and number of subjects in a group) will be computed by treatment group and separately for subjects who do/do not experience clinically significant disease reactivation at each specified time point. Summary statistics will be plotted versus time at the relevant time points. Plots for individual subjects will also be created.

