# 7.4.2. Changes in C3, C4, and anti-dsDNA Levels

**Endpoint**: C3, C4, and anti-dsDNA are run at baseline and every follow-up visit, including any Flare or Endpoint visits, during the course of the 60 week study period and run by a central laboratory. Change from baseline will be calculated for each test and time point.

Specifically, change from baseline in levels of C3, C4, and anti-dsDNA at Week 20, the time of first flare, and immediately prior to first flare will be analyzed.

Version: 1.0 Page 29 of 48

**Analysis**: Descriptive statistics (mean, standard deviation, median, minimum, maximum and number of subjects in a group) will be computed by treatment group and separately for subjects who do/do not experience clinically significant disease reactivation at each specified time point. Summary statistics will be plotted versus time at the relevant time points. Plots for individual subjects will also be created.

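### Week 20 C3, C4 and anti-dsDNA summaries are split by reactivation over the whole study, so the Week 20 rows cannot be read as predictors of later reactivation

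*SAP*

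**What the plan says.** SAP 7.4.1 states that "levels of C3, C4, and anti-dsDNA at Baseline, Week 20, at the time of first flare, and immediately prior to first flare will be analyzed". SAP 7.4.2 does the same for "change from baseline in levels of C3, C4, and anti-dsDNA at Week 20, the time of first flare, and immediately prior to first flare". In both sections the summaries are given by treatment group and "separately for subjects who do/do not experience clinically significant disease reactivation at each specified time point", together with plots over time and plots for individual subjects. Protocol 8.3.3 carries the same split.

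The grouping variable comes from SAP 7.2.1: a yes/no indicator of whether the subject "has met the primary endpoint of clinically significant disease reactivation between Day 0 and Week 60". SAP 7.1.2 keeps all data whatever the time of assessment. Neither 7.4.1 nor 7.4.2 limits the Week 20 rows to subjects who are still free of reactivation.

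The purpose is set in the protocol. Section 2.2.3 seeks marker characteristics "present at Week 20 or changes in those characteristics from baseline to Week 20 that are associated with an increased risk of flare". Section 6.3.1 says C3, C4 and anti-dsDNA will be analysed to "define the utility of the markers in predicting which subjects will meet the primary endpoint of clinical disease activation".

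**The concern.** A marker can predict an event only if it is measured before the event. Under Protocol 5.10.1, a subject who reactivates stops study drug, is treated at the investigator's discretion and continues study visits. Table 6.1, note 12, says that visits and assessments go on as scheduled. By definition the endpoint also involves steroid or immunosuppressant escalation. A subject who reactivates at Week 12 therefore still gives a Week 20 sample, and that sample reflects the flare and its treatment.

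That value sits in the reactivator column of the Week 20 row, beside values from subjects who reactivate later. A difference from non-reactivators could be a true early signal, an effect of active disease, or an effect of treatment, and the table cannot separate these. At stake is the Week 20 part of the mechanistic objective: a null marker could look informative, or an informative one could be diluted.

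**Working it through.** **Which rows are affected**

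| Time point in SAP 7.4.1 / 7.4.2 | Position relative to reactivation | Affected? |
|---|---|---|
| Baseline | Before all events | No |
| Immediately before first flare | Before the event, because reactivation requires a flare | No |
| First flare | At the flare, by design; not offered as an early predictor | No |
| Week 20, and change to Week 20 | Before the event for some reactivators, after it for others | Yes |

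**Number of reactivators.** SAP section 12 reports 8 of the first 80 subjects: 8/80 = 0.10, as stated there. Applied to the planned 120, this is 0.10 × 120 = 12 reactivators and 108 others, ignoring dropout.

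**Share before Week 20 (f).** The documents give none, so f is assumed to lie between 1/3 and 2/3. As a reference, a constant hazard with 10% risk by Week 60 gives f = (1 − 0.9^(20/60)) / 0.10 = 0.345. Protocol 3.1.1 says "we anticipate that most flares will occur early in the study", which points higher, but it speaks of flares and not of reactivations.

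**Size for a marker with no predictive value.** Let the event or its treatment shift the marker by δ SD (assumed), and let every early reactivator supply a Week 20 value. The reactivator mean is f × δ + (1 − f) × 0, so the spurious difference is f × δ. The last column is 12 × (1 − f).

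| f | Early reactivators (12 × f) | Difference at δ = 0.5 SD | Reactivators left after a Week 20 landmark |
|---|---|---|---|
| 1/3 | 4 | 0.17 SD | 8 |
| 1/2 | 6 | 0.25 SD | 6 |
| 2/3 | 8 | 0.33 SD | 4 |

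The sign follows δ. Active disease and its treatment may move a marker in opposite directions, so the sign is unknown.

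**The opposite error.** If the true pre-event difference is 1 SD and treated early reactivators have returned to normal, the unrestricted row shows (1 − f) × 1 SD, that is 0.67 SD down to 0.33 SD.

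**Precision.** The standard error of the unrestricted difference is √(1/12 + 1/108) = 0.30 SD. After a landmark with 6 later reactivators it is √(1/6 + 1/108) = 0.42 SD.

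**The case against.** The strongest reply is that these are descriptive tables. No test, model or cut-off is planned, and Protocol 8.3.3 places such statistics before any modelling. The same SAP sections include Baseline values, pre-flare values and individual plots. With about 12 reactivators, a careful reader could see from those plots which Week 20 values came after the event. All of this stands and limits the consequence to misreading. It does not remove the problem, because neither document specifies another analysis, or a landmark, for the Week 20 objective for these markers.

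The wording of the split could also mean reactivation status at each time point. That reading gives a cross-sectional comparison at Week 20, which shows no prediction either.

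The timing evidence is indirect. Reactivation needs more than a flare, and Protocol 1.5 says only about 40% of SELENA-SLEDAI flares require treatment. The withdrawal arm is still tapering until Week 12. Under Protocol 5.10.1.1, visits after discontinuation continue only where possible, so some early reactivators may have no Week 20 value. These points stand: the number affected is not known.

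The illustrated 0.17 to 0.33 SD is also small against a standard error of 0.30 SD, roughly half to just over one standard error. That is fair, but the distortion is systematic and would not average out.

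Finally, removing only earlier reactivators leaves in subjects who flared and were treated before Week 20 without meeting the endpoint. This is correct, and the fix deals with it.

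**Conclusion.** The point holds for the Week 20 levels and the changes from Baseline to Week 20. As written, those rows cannot be read as Week 20 predictors of later reactivation. The illustration (4 to 8 of about 12 reactivators, and 0.17 to 0.33 SD) rests on three assumptions: the 10% pooled rate carries to 120 subjects, 1/3 to 2/3 of reactivations come before Week 20, and the marker shifts by 0.5 SD. The true size and direction are unknown.

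A reader might infer more than the documents support:

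- That the marker analysis as a whole cannot show prediction. Baseline and pre-flare summaries precede the event.
- That the plan will produce a false marker for deciding who can stop MMF. Protocol 1.5.5 ties that question to baseline predictors, and no passage gives these tables a decision role.
- That most reactivations are early. Protocol 3.1.1 says this of flares only.
- That an error rate is inflated. No test is planned.

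**What to change.** In SAP 7.4.1 and 7.4.2, for the Week 20 levels and the changes to Week 20:

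- Include only subjects on study with no reactivation dated on or before the Week 20 visit, using the SAP 7.2.1 dating rule.
- Group them by reactivation after Week 20 through Week 60.
- Show earlier reactivators in a separate column.
- Repeat the display in subjects with no SELENA-SLEDAI flare by Week 20, because the Protocol 2.2.3 objective refers to flare.
- Keep the Baseline analysis on all subjects.

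Because Protocol 8.3.3 has the same unrestricted split, record the change in SAP section 12. The fix needs SAP wording only and uses samples already scheduled. The cost is fewer events in the Week 20 comparison, about 4 to 8 of 12 under the range above, and possibly fewer in the flare-free repeat. The comparison should therefore stay descriptive; even with the landmark it would not establish prediction.

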# 7.4.2. Changes in C3, C4, and anti-dsDNA Levels

**Endpoint**: C3, C4, and anti-dsDNA are run at baseline and every follow-up visit, including any Flare or Endpoint visits, during the course of the 60 week study period and run by a central laboratory. Change from baseline will be calculated for each test and time point.

Specifically, change from baseline in levels of C3, C4, and anti-dsDNA at Week 20, the time of first flare, and immediately prior to first flare will be analyzed.

Version: 1.0 Page 29 of 48

**Analysis**: Descriptive statistics (mean, standard deviation, median, minimum, maximum and number of subjects in a group) will be computed by treatment group and separately for subjects who do/do not experience clinically significant disease reactivation at each specified time point. Summary statistics will be plotted versus time at the relevant time points. Plots for individual subjects will also be created.

# 7.4.3. Antibody Levels

**Endpoint**: Antibody levels, including, but not limited to Sm, ribonucleoprotein (RNP), SSA/Ro, & SSB/La are assessed at the Baseline, Week 60, and if needed, the flare visit and run by a central laboratory.

**Analysis**: Descriptive statistics (mean, standard deviation, median, minimum, maximum and number of subjects in a group) and/or a summary of categorical response (positive, negative, indeterminate, etc.) will be computed by treatment group for each antibody result. Summary statistics will be plotted versus time at the relevant time points as applicable.

# 7.5. Examination of Subgroups

Secondary analyses of the primary and secondary objectives may be conducted for the following subgroups, including, but not limited to:

- Age
- Race/ethnicity
- Disease manifestation (renal disease/extra-renal disease), as defined in Section 7.3.5.
- SLE duration (< 5 years / ≥ 5 years)

- Baseline MMF dosing group (<2000 mg per day / ≥ 2000 mg per day)
- Baseline autoantibody status

Additionally, exploratory analyses of subgroups defined through the mechanistic and immunological studies may also be conducted.

#### 8. SAFETY EVALUATION

# 8.1. Overview of Safety Analysis Methods

All safety analyses will be carried out using the safety sample defined in Section 4.2 unless otherwise noted. Missing safety information will not be imputed. These analyses will not be stratified by site. All safety comparisons and associated p-values are considered exploratory, not as formal tests of hypothesis. As such, no adjustments will be made for multiple comparisons and all p-values must be interpreted cautiously.

Listings will be prepared for all safety measurements. All listings will be sorted in order of treatment, subject identifier (ID), and time of assessment (e.g., visit, time, and/or event).

#### 8.2. Extent of Exposure

Extent of exposure during the trial will be described for MMF. Exposure will be measured as the total number of days on medication defined as last dose date – first dose date + 1 and the cumulative dose of that medication defined as the sum of the doses in mg taken up to the relevant cutoff date. Exposure will be summarized until a subject stops taking study provided MMF.

Version: 1.0 Page 30 of 48

#### 8.3. Adverse Events

All AEs will be classified by system organ class (SOC) and preferred term, according to a standardized thesaurus (Medical Dictionary for Regulatory Activities [MedDRA] version 16.1). The severity of AEs will be classified using the National Cancer Institute's (NCI's) Common Toxicity Criteria for Adverse Events (CTCAE) version 4.0. Each AE is entered on the electronic case report form (eCRF) once at the highest severity. As such, no additional data manipulation is needed to identify events.

Adverse events will be collected from the time the subject signs the informed consent until he/she initiates study intervention or until he/she is determined to be ineligible to receive study intervention, if the investigator determines that the AE is related to a study-mandated procedure, treatment, or change in treatment.

Regardless of whether the above is applicable, for all participants: AEs will be collected from the time of initiation of study intervention (i.e., the administration of the first dose of study-supplied MMF as defined in Protocol Section 6.4.2, *Baseline/Randomization Visit*) until he/she completes study participation or until 30 days after he/she prematurely withdraws (without withdrawing consent) or is withdrawn from the study.

Treatment-emergent AEs will be identified as those with an onset date on or after the first dose of study medication as well as those with onset before first dose but that continued and worsened in severity after first dose. If the start of the AE in relation to the start of study medication cannot be established (e.g., the start date for the AE is missing), then the AE will be considered treatment-emergent. All data tabulations will be of only treatment-emergent events while non-treatment-emergent AEs will be listed separately, unless otherwise noted.

Indicator variables will be derived for the following categories of AEs: infections, malignancies, BILAG A flares, and severe SELENA-SLEDAI flares. Yes/no questions for each of these types of events are included on the *Adverse Events* CRF page.

Relationship to study treatment will be categorized as either treatment related (possibly, probably, or definitely related to study medication) or unrelated (unlikely related or unrelated).

An overall summary table will be developed to report the number of events and the number and percentage of subjects having at least one event in the following categories:

- AEs
- AEs indicated as serious
- AEs that lead to study drug discontinuation
- AEs with an outcome of death
- AEs that were reported as being related to MMF
- AEs that were reported as being related to SLE
- AEs reported by maximum severity
- AEs that are BILAG A flares
- AEs that are severe SELENA-SLEDAI flares

Version: 1.0 Page 31 of 48

In addition, AEs classified by MedDRA SOC and preferred term will be summarized for each treatment group and overall for each of the following:

- All AEs
- AEs by maximum severity
- AEs by relationship to study drug

Summary tables will present the total number of events as well as the number and percentage of subjects experiencing the events. If a subject experiences the same AE on multiple occasions, the event will be counted once for each occurrence when reporting the number of AEs. When reporting the number of subjects experiencing the events, a subject will only be counted once if they experience an event within the particular SOC or preferred term. Percentages will be based on the number of subjects in the safety population. To account for differential duration of study participation among subjects, the summaries will include the event rate (i.e. number of events per person-time) in addition to the number and percent of events and subjects experiencing events.

Separate data listings will be provided for treatment-related AEs and AEs leading to study drug discontinuation.

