### 5.3 Administration of Study Product

Subjects on the MMF maintenance arm will receive a new supply of MMF at each study visit from Baseline through Week 48.

Subjects on the MMF withdrawal arm will receive a new supply of MMF at each study visit from Baseline through Week 8.

For additional information on criteria for withholding or discontinuing study product, see Section 5.4, *Prevention and Management of Toxicity for MMF*.

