#### 5.10 Treatment Discontinuation and Subject Withdrawal

#### 5.10.1 Study Treatment Discontinuation

Study drug provided by the sponsor will be discontinued for any individual subject under the following conditions:

- 1. At any time during the study at the request of the subject or subject's guardian.
- 2. If investigators or NIAID determine that the subject's health, safety, and/or wellbeing are threatened.
- 3. For either disease activity or toxicity guidelines as outlined below:
  - Disease Activity: If the subject meets the primary endpoint of clinically significant disease reactivation, the study drug will be discontinued and subject treated at the discretion of the investigator per Section 5.3.1, *Administration of Study Product in Response to SLE Reactivation*, but the subject will continue study visits. Clinically significant disease reactivation is defined in Section 3.2 *Description of Primary Endpoint*.
  - Toxicity or Infection:
    - If the subject must discontinue study drug for more than 14 sequential days due to ongoing, suspected MMF toxicity, then study drug will be discontinued, but the subject will continue study visits.
    - If the subject has study drug withheld for a cumulative total of 28 days or greater in the setting of multiple or recurrent MMF toxicity, study drug will be discontinued, but the subject will continue study visits.
- 4. If the subject is female and becomes pregnant.
- 5. Subject non-compliance with treatment regimens or failure to keep appointments.

Subjects who discontinue protocol-specified treatment requirements will be treated as medically indicated according to discretion of the treating physician.

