#### **8.3** Description of the Analyses

In presenting data from this trial, continuous data will be summarized in tables listing the mean, standard deviation or standard error, median, and number of subjects in a group. Categorical data will be summarized in tables listing the frequency and the percentage of subjects in a group. These summaries will be presented separately for subjects on the two treatment arms.

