#### 6.2. Treatment Adherence

Subjects will be randomized to one of the two study treatment arms below.

- MMF maintenance arm: These subjects will continue MMF treatment (1000-3000 mg/day) for the rest of their study participation (up to Week 60).
  - Baseline MMF dose = 3000 mg/day
    - Up to 60 weeks on 3000mg/day MMF
  - Baseline MMF dose = 2500 mg/day to 2750 mg/day
    - Up to 60 weeks on 2500mg/day MMF
  - Baseline MMF dose = 2000 mg/day to 2250 mg/day
    - Up to 60 weeks on 2000mg/day MMF
  - Baseline MMF dose = 1500 mg/day to 1750 mg/day
    - Up to 60 weeks on 1500mg/day MMF
  - Baseline MMF dose = 1000 mg/day to 1250 mg/day
    - Up to 60 weeks on 1000mg/day MMF
- MMF withdrawal arm: These subjects will taper off MMF over 12 weeks and remain off MMF for the rest of their study participation (up to Week 60 or until the primary endpoint of disease reactivation is met, whichever comes first).
  - Baseline MMF dose = 3000 mg/day
    - Four weeks on 1000 mg MMF twice a day (BID)
    - Four weeks on 1000mg (morning) & 500mg MMF (evening) QD
    - Four weeks on 500 mg MMF BID
    - Up to 48 weeks on no MMF
  - Baseline MMF dose = 2500 mg/day to 2750 mg/day
    - Four weeks on 1000mg MMF BID
    - Four weeks on 1000mg (morning) & 500mg (evening) MMF QD
    - Four weeks on 500 mg MMF BID
    - Up to 48 weeks on no MMF
  - Baseline MMF dose = 2000 mg/day to 2250 mg/day
    - Four weeks on 1000mg (morning) & 500mg (evening) MMF QD
    - Four weeks on 500mg MMF BID
    - Four weeks on 500 mg MMF QD
    - Up to 48 weeks on no MMF
  - Baseline MMF dose = 1500 mg/day to 1750 mg/day
    - Four weeks on 500mg MMF BID
    - Four weeks on 500 mg MMF BID
    - Four weeks on 500 mg MMF QD
    - Up to 48 weeks on no MMF
  - Baseline MMF dose = 1000 mg/day to 1250 mg/day

Version: 1.0 Page 14 of 48

- Four weeks on 500 mg MMF BID
- Four weeks on 500 mg MMF QD
- Four weeks on 500 mg MMF QD
- Up to 48 weeks on no MMF

Prescribed MMF doses for subjects in the study will be collected on the Study Drug Dose Log CRF page. Information on this page includes dates of dose changes, prescribed doses (including a "zero" dose when a subject completes tapering), and reasons for dose changes. Bottles of MMF dispensed along with pill counts will be collected on the Study Drug Accounting Log CRF page. This page includes information on the number of bottles dispensed, number of pills in the bottle, dates dispensed and returned, pills returned, and pills lost.

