For both treatment arms, the total number of expected pills to be taken will be derived based on a subject's prescribed MMF dose, taken from the Study Drug Dose Log CRF page, and duration of time in the study.

The actual number of pills taken will be derived based on data on the Study Drug Accounting Log CRF page. Given then number of bottles dispensed and number of pills in the bottles, actual pills counts will be derived based on the number of pills returned and number of pills lost. It will be assumed that any pills not returned or reported as lost by a subject will have been taken by the subject. Compliance will be calculated over the 12 week taper period for the Withdrawal arm and over the 60 week study period for the Maintenance arm.

Compliance will be calculated as:

$$\% \ \textit{Compliance} = \frac{\textit{Total Number of Actual Pills Taken}}{\textit{Expected Number of Pills Taken}} \times 100$$

For subjects who terminate early from the study or who discontinued study-provided MMF early, compliance will only be calculated for the time in which the subject is taking study-provided MMF.

Version: 1.0 Page 15 of 48

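### The SAP 8.3 row for adverse events that stop study drug is not comparable between arms: withdrawal subjects can enter it for 12 weeks, maintenance subjects for up to 60

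*SAP*

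**What the plan says.** The overall adverse event table in SAP 8.3 gives the number of events, and the number and percentage of subjects, for several categories. One of them is "AEs that lead to study drug discontinuation". Percentages use all subjects in the safety population. Events are collected from first dose "until he/she completes study participation or until 30 days after he/she prematurely withdraws", so collection does not end when study drug ends. On differing follow-up, the SAP says: "To account for differential duration of study participation among subjects, the summaries will include the event rate", defined as events per person-time.

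The time during which there is study drug to stop differs by arm:

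- Protocol 5.3: "Subjects on the MMF withdrawal arm will receive a new supply of MMF at each study visit from Baseline through Week 8".
- SAP 6.2, for every withdrawal schedule after the taper: "Up to 48 weeks on no MMF".
- SAP 6.2 on adherence: "Compliance will be calculated over the 12 week taper period for the Withdrawal arm and over the 60 week study period for the Maintenance arm".

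Protocol 5.10.1 shows what discontinuation refers to: "Study drug provided by the sponsor will be discontinued for any individual subject under the following conditions". It concerns sponsor-provided MMF.

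The SAP sentence that introduces the overall table does not itself say that it is split by arm. That follows from the general rule in Protocol 8.3: "These summaries will be presented separately for subjects on the two treatment arms".

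**The concern.** After Week 12 a withdrawal subject has no study drug left to discontinue. The same adverse event at Week 30 could count in this row for a maintenance subject and could not count for a withdrawal subject, whatever its cause.

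Readers commonly take such a row as evidence on tolerability. Protocol 1.5 says the trial is meant to compare the risks and benefits of continuing and withdrawing MMF, and Protocol 1.5.4 gives the control arm the purpose of comparing drug toxicity on and off MMF. If the row shows far fewer discontinuations after withdrawal, a reader cannot tell how much reflects less toxicity and how much reflects having had nothing to stop for 48 of 60 weeks.

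**Working it through.** **Is there a figure to reproduce?** No. Neither document states an expected number or rate of adverse events leading to discontinuation. The durations agree with each other: 60 − 12 = 48 weeks off drug, as SAP 6.2 states.

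**Inputs from the documents.** 12 weeks on study drug in the withdrawal arm and up to 60 in maintenance (SAP 6.2); 60 subjects per arm, from 120 randomized 1:1 (Protocol 3.1); maintenance reactivation risk 0.05 to 0.15 (Protocol 8.1).

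**Assumed.** The 60-week risk P60 of such an event on MMF, varied from 5% to 20%, and a weekly hazard h that is constant while on drug and equal in both arms.

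**Step 1: subjects in the row.** h = −ln(1 − P60)/60, and P12 = 1 − exp(−12h) = 1 − (1 − P60)^(12/60).

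| P60 (maintenance) | P12 (withdrawal) | Ratio | Expected subjects of 60 |
|---|---|---|---|
| 5% | 1.02% | 4.90 | 3.0 vs 0.61 |
| 10% | 2.09% | 4.80 | 6.0 vs 1.25 |
| 15% | 3.20% | 4.69 | 9.0 vs 1.92 |
| 20% | 4.36% | 4.58 | 12.0 vs 2.62 |

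For rare events the ratio tends to 60/12 = 5.

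**Step 2: the planned rate.** Planned participation is 60 weeks in both arms, and Protocol 5.10.1.1 asks subjects who stop drug for disease activity or toxicity to continue visits where possible. At P60 = 10% the ratio of rates is (0.10/60)/(0.0209/60) = 4.80, so the imbalance is unchanged.

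**Step 3: time on drug as denominator.** At P60 = 10%, h = 0.10536/60 = 0.001756 per week. Mean weeks on drug are 0.10/0.001756 = 56.9 and 0.02085/0.001756 = 11.9. Both rates equal h, so the ratio is 1.0.

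**Step 4: sensitivity to the assumptions.**

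- Reactivation of 5% to 15% as a competing reason to stop drug, with discontinuation risks of 2% to 20%: ratio 4.3 to 4.9.
- Hazard in the first 12 weeks twice the later hazard, rare events: (12×2 + 48)/(12×2) = 3.0.
- Hazard proportional to dose, rare events: the ratio of cumulative doses. At baseline 3000 mg/day, 60×3000 / [4×(2000+1500+1000)] = 180,000/18,000 = 10. At 1000 mg/day, 60×1000 / [4×(1000+500+500)] = 60,000/8,000 = 7.5. The other baseline levels lie between 8.3 and 10.

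**Step 5: what can enter after Week 12.** Protocol 7.5.1 has flares reported as adverse events, and Protocol 5.10.1 stops study drug when the primary endpoint is met. Protocol 5.3.1 lets some of these subjects stay on study-provided MMF, and the two sections should be reconciled. Under either, a flare after Week 12 can lead to discontinuation of study drug only in the maintenance arm. The same holds for any event unrelated to MMF.

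**The case against.** The strongest reply is that withdrawal is the intervention. The trial compares 60 weeks of MMF with a taper followed by none, and Protocol 2.2.2 asks for the effect of withdrawal on safety and drug-related toxicity. Five times the exposure at an equal weekly hazard is then a real difference in cumulative toxicity, and an on-drug rate shown alone would hide it. This stands, and it is why the planned counts should stay. It does not cover events unrelated to MMF, or flares, which drop out of the withdrawal arm's row after Week 12 only because there is no drug to stop.

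It is also true that the row is descriptive. It is not among the nine secondary safety endpoints in SAP 8.3.1, so neither Fisher's test nor Poisson regression applies to it. SAP 8.2 summarizes days on MMF, SAP 5.1 presents reasons for stopping early, and SAP 8.3 provides a listing of these events, so a careful reader could rebuild the split. That limits the consequence, but the summary row itself still lacks a comparable denominator.

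Participation is up to 60 weeks and may differ by arm through early termination. The planned rate handles that, but not the difference in time on drug.

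A reader might infer that maintenance would show five times as many such events with no true difference, or that the table is simply biased against MMF. The documents support neither. The factor of five needs rare events and a constant, dose-independent hazard, while most withdrawal subjects are on reduced doses during the taper. Part of the contrast is also a genuine effect of the assigned strategy.

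**Conclusion.** The point holds as a limited one about presentation. As planned, this row mixes a real effect of shorter MMF exposure with a structural difference in opportunity, and the participation-based rate does not separate them. The size cannot be fixed from the documents, because they give no discontinuation rate and no hazard shape. The ratios of 4.6 to 4.9, about 3, and 7.5 to 10 are illustrations under the stated assumptions. A roughly constant hazard is plausible, because subjects have already taken MMF for at least one or two years at entry, but that is a judgement.

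The primary analysis is unaffected. So are the nine secondary safety endpoints, which do not depend on there being study drug to stop. Withdrawal-arm flares also remain visible in the disease activity endpoints and, if severe or BILAG A, in their own rows of the same table.

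**What to change.** In SAP 8.3, for this category only:

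1. Keep the planned counts and percentages by arm.
2. Add the event rate per person-time on study-provided MMF, using the first and last dose dates already derived for SAP 8.2.
3. Show Weeks 0-12 for both arms.
4. Label Weeks 12-60 as maintenance arm only, with a note that withdrawal subjects had no study drug to discontinue.

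The cost is a few lines of SAP text and one or two extra table columns; no new data are needed. The downside is sparse Weeks 0-12 counts: about 0.6 to 1.9 subjects per arm of 60 at 60-week risks of 5% to 15%. That window also compares full-dose with tapering subjects, so it should be read alongside the other columns and not alone.
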